### **6.6.2.1      Warnings, Precautions, and Management Guidelines for Adverse Events Associated with Cabozantinib Treatment**

The most frequent AEs experienced by  $\geq 20\%$  of subjects treated with cabozantinib in descending order of frequency were diarrhea, fatigue, nausea, decreased appetite, vomiting, weight decreased, PPE, constipation, hypertension, dysgeusia, dysphonia, and asthenia. For a full description of the safety profile of cabozantinib, refer to the cabozantinib Investigator Brochure.

Other medically important but less frequent AEs include arterial thrombotic AEs (eg, TIA, and MI) and venous thrombotic AEs (eg, DVT and PE), severe hemorrhagic events, proteinuria, wound healing complications, GI perforation, abscesses including intra-abdominal and pelvic abscess, GI and non-GI fistula formation, osteonecrosis, and reversible posterior leukoencephalopathy syndrome (RPLS; preferred term: posterior reversible encephalopathy syndrome).

Adverse events associated with laboratory test abnormalities that were experienced by  $\geq 5\%$  of cabozantinib-treated subjects in descending order of frequency were anemia, AST increased, ALT increased, hypothyroidism, hypokalemia, hypomagnesemia, thrombocytopenia, hypocalcemia, hypophosphatemia, lactate dehydrogenase (LDH) increased, lipase increased, neutropenia, hyponatremia, alkaline phosphatase (ALP) increased, leukopenia, and hyperglycemia.

Adverse events may occur within the first few weeks in the course of treatment with cabozantinib, as cabozantinib is expected to reach steady state exposure at approximately 2 weeks following first dose. Events that generally have an early onset include hypocalcemia, hypokalemia, thrombocytopenia, hypertension, PPE, abdominal pain, mucosal inflammation, constipation, diarrhea, and vomiting. Adverse events should be managed with supportive care at the earliest signs of toxicity. Dose reductions and treatment interruptions should be considered. Dose reductions are recommended for events that, if persistent, could become serious or intolerable ([Table 6-4](#)).

Cabozantinib should be discontinued for the following AEs: visceral perforation or fistula formation, severe hemorrhage, serious arterial thromboembolic events, nephrotic syndrome, hypertensive emergency, persistent uncontrolled hypertension despite optimal medical management, and RPLS.

#### **6.6.2.1.1 Gastrointestinal Disorders**

**Gastrointestinal (GI) perforation, GI fistula, and intra-abdominal and pelvic abscess:** After starting treatment with cabozantinib, subjects should be monitored for early signs of GI perforation such as abdominal pain, nausea, emesis, constipation, and fever especially if known risk factors for developing GI perforation or fistula (Turnage and Badgwell 2012) are present. Discontinue cabozantinib and initiate appropriate management in subjects who have been diagnosed with GI perforation or fistula.

**Diarrhea:** Subjects should be instructed to notify their physician immediately at the first signs of poorly formed or loose stool or an increased frequency of bowel movements. Guidelines for the evaluation and management of diarrhea are shown in [Table 6-6](#). Administration of antidiarrheal/antimotility agents is recommended at the first sign of diarrhea as initial management. Some subjects may require concomitant treatment with more than one antidiarrheal agent. When therapy with antidiarrheal agents does not control the diarrhea to tolerable levels, cabozantinib should be temporarily interrupted or dose reduced. When the diarrhea is controlled, retreatment with cabozantinib may be acceptable per investigator decision. In addition, general supportive measures should be implemented such as continuous oral isotonic hydration, correction of fluid and electrolyte abnormalities, small frequent meals, and stopping lactose-containing products, high-fat meals, and alcohol.

Recurrent or prolonged diarrhea can be associated with anal or perianal skin erosions which increase the risk for anal abscesses, fistulas, or proctitis. Good personal hygiene should be emphasized. Regular examinations of the perianal region should be performed whenever diarrhea has occurred during treatment with cabozantinib. Infections of the perianal region should be treated per local guidelines.

Following improvement in diarrhea, dose re-escalation should follow the guidelines listed in [Section 6.6.2](#).

**Table 6-6: Management of Diarrhea Associated with Cabozantinib**

Status	Management
Tolerable Grade 1-2 (duration < 48 h)	

Continue with study treatment and consider dose reduction

Initiate treatment with an antidiarrheal agent (eg, loperamide 4 mg followed by 2 mg after each episode of diarrhea [maximum: 16 mg loperamide per day])

Dietary modifications (eg, small lactose-free meals, bananas and rice)

Intake of isotonic fluids (1-1.5 L/day)

Re-assess after 24 hours:

Diarrhea resolving to baseline bowel habits: gradually add solid foods and discontinue or decrease antidiarrheal treatment after 12 h diarrhea-free interval

Diarrhea not resolving: Continue/resume antidiarrheal treatment

Intolerable Grade 2, Grade 2 > 48 h, or $\geq$ Grade 3	

Interrupt study treatment

Ask subject to attend clinic

Rule out infection (eg, stool sample for culture)

Administer antibiotics as needed (eg, if fever or Grade 3-4 neutropenia persists > 24 h)

Administer fluids (1-1.5 L/day orally or IV, as appropriate) for hydration or to correct electrolyte abnormalities

For Grade 3-4 or complicated lower-grade diarrhea consider hospitalization and IV hydration

Re-assess after 24 h

Diarrhea resolving to baseline bowel habits or Grade <math>\leq</math> 1: consider restarting study treatment at reduced dose

Diarrhea not resolving: Start and/or continue antidiarrheal treatment (eg, loperamide 4 mg followed by 2 mg after each episode of diarrhea [maximum: 16 mg loperamide per day]). Consider starting second line antidiarrheal or referral to gastroenterologist

**Nausea and vomiting:** Antiemetic agents are recommended as clinically appropriate for treatment or prophylaxis of nausea and vomiting, along with supportive care. Dehydration and electrolyte abnormalities may be associated with vomiting and monitoring for and correction of fluid and electrolyte disturbances should be implemented. Antiemetic medications should be assessed for potential drug interactions (refer to [Section 7.3](#) for further details).

#### 6.6.2.1.2 Non-Gastrointestinal Fistula

Complications from radiation therapy especially of the thoracic cavity including mediastinum have been identified as a possible predisposing risk factor for non-GI fistula formation in subjects undergoing treatment with VEGF pathway inhibitors.

CONFIDENTIAL

Protocol XL184-313 Protocol Amendment 3.0  
Page 93 of 193

Discontinue cabozantinib and initiate appropriate management in subjects who have been diagnosed with a non-GI fistula.

#### **6.6.2.1.3 Hemorrhage**

Hemorrhagic events, including serious and sometimes fatal events, have been reported with cabozantinib. Subjects should be monitored for bleeding events with serial complete blood counts and physical examination while on study. The risk of hemorrhage in cabozantinib-treated subjects with brain metastases has not been thoroughly analyzed. Subjects enrolled with treated and stable brain metastases should be monitored with a high index of suspicion if symptoms that could be due to a CNS hemorrhage occur.

Cabozantinib should be discontinued in subjects with serious and life-threatening bleeding events or recent hemoptysis ( $\geq 2.5$  mL of red blood).

#### **6.6.2.1.4 Thromboembolic events**

Thromboembolic events are frequent in cancer subjects due to procoagulant changes induced by the malignancy or anti-cancer therapy. Deep vein thrombosis (DVT) and pulmonary embolism (PE) have been observed in clinical studies with cabozantinib, including fatal events. Subjects who develop a PE and/or DVT should have study treatment interrupted until therapeutic anticoagulation is established. Treatment with cabozantinib may be resumed in subjects with PE or DVT if it is determined that the event is uncomplicated and that the subject is deriving clinical benefit from cabozantinib treatment and that anticoagulation does not place them at a significant risk that outweighs the benefit of resuming treatment per discretion of the Investigator and according to individual protocols. Low molecular weight heparins are the preferred management for thrombotic events; oral anticoagulants (eg, warfarin or other coumarin-related agents, direct thrombin or direct FXa inhibitors, or antiplatelet agents, or chronic use of aspirin above low dose levels for cardioprotection per local applicable guidelines) are not allowed.

Arterial thrombotic events (eg, TIA, myocardial infarction) have been observed in studies with cabozantinib. Further treatment with cabozantinib should be discontinued in subjects who develop an acute myocardial infarction, cerebral infarction, or any other clinically significant arterial thromboembolic complication.

#### **6.6.2.1.5 Hypertension**

[Table 6-7](#) provides treatment guidelines for hypertension deemed related to cabozantinib. Blood pressure should be monitored in a constant position visit to visit, either sitting or supine in a relaxed setting. Decisions to reduce or interrupt the dose of study treatment must be based on BP

readings taken by a medical professional and must be confirmed with a second measurement at least 5 minutes following the first measurement.

Cabozantinib should be discontinued in subjects with hypertensive emergency.

**Table 6-7: Management of Hypertension Associated with Cabozantinib**

Criteria for Dose Modifications	Treatment/Cabozantinib Dose Modification
> 150 mm Hg (systolic) a and < 160 mm Hg OR > 100 mm Hg (diastolic) and < 110 mm Hg	
 
Optimize antihypertensive medications by adding new or additional antihypertensive medications and/or increase dose of existing medications.
 
Reduce cabozantinib treatment by one dose level if optimal antihypertensive therapy (usually to include 3 agents) does not result in BP <150 mm Hg systolic and <100 mm Hg diastolic
 
If subject is symptomatic interrupt cabozantinib treatment
 

≥ 160 mm Hg (systolic) OR ≥ 110 mm Hg (diastolic)	
 
Reduce cabozantinib by one dose level or interrupt cabozantinib treatment per investigator discretion
 
Add new or additional anti-hypertensive medications and/or increase dose of existing medications and monitor subject closely for hypotension. If optimized antihypertensive therapy (usually to include 3 agents) does not result in BP < 150 mm Hg systolic and < 100 mm Hg diastolic, cabozantinib treatment should be dose reduced further or interrupted
 
Cabozantinib treatment should be dose interrupted if upper limits of systolic BP (≥ 160 mm Hg) are sustained and not adequately manageable or if systolic BP is > 180 mm Hg or sustained diastolic BP > 110 mm Hg, or if subject is symptomatic
 
Re-start cabozantinib treatment at the most tolerable dose and re-escalate only if BP falls to and is sustained at < 150 mm Hg systolic and < 100 mm Hg diastolic
 

Hypertensive emergency b	
 
Discontinue cabozantinib treatment
 

BP, blood pressure.

a The investigator may decide to initiate or adjust antihypertensive treatment at a lower threshold than systolic BP >150 mm Hg or diastolic BP > 100 mm Hg based on their clinical judgment and assessment of the individual subject.

b Hypertensive emergency is defined as uncontrolled elevated BP with clinical evidence of progressive or impending end-organ damage (eg, myocardial infarction/ischemia, intracranial hemorrhage, cerebral ischemia, pulmonary edema, encephalopathy, kidney damage).

CONFIDENTIAL

Protocol XL184-313 Protocol Amendment 3.0  
Page 95 of 193

#### **6.6.2.1.6 Stomatitis and Mucositis**

Preventive measures may include a comprehensive oral examination to identify and treat any potential risk for complications before study treatment is initiated. Appropriate correction of local factors should be instituted as indicated, such as modification of ill-fitting dentures and appropriate care of gingivitis. During treatment with cabozantinib, good oral hygiene and standard local treatments such as non-traumatic and non-irritating cleansing, and oral rinses (eg, with a weak solution of salt and baking soda) should be maintained. Lips should be kept moisturized with lip balm. The use of lipstick, lip-gloss, and Vaseline should be avoided.

Local treatment should be instituted at the earliest onset of symptoms. Obtain bacterial/viral culture if oral infection is suspected and treat infection as clinically indicated.

#### **6.6.2.1.7 Skin and Subcutaneous Tissue Disorders**

Wound healing and surgery: Cabozantinib has the potential to cause wound healing complications and wound dehiscence, which may even occur long after a wound has been considered healed. Therefore, surgical and traumatic wounds must not only be completely healed prior to starting cabozantinib treatment but must also be monitored for wound dehiscence, wound infection and other signs of impaired wound healing while the subject is being treated with cabozantinib. If dehiscence occurs, cabozantinib treatment should not be restarted until complete healing has taken place.

Treatment with cabozantinib should be stopped at least 28 days prior to scheduled surgery (for tumor biopsies at least 10 days before the procedure). The decision to resume treatment with cabozantinib after surgery should be based on clinical judgment of adequate wound healing.

Palmar-plantar erythrodysesthesia (PPE; also known as hand-foot syndrome), skin rash (including blister, erythematous rash, macular rash, skin exfoliation, dermatitis acneiform, and papular rash), pruritus, dry skin, erythema, pigmentary changes, and alopecia have been reported with cabozantinib. All subjects on study should be advised on prophylactic measures including the use of emollients, removal of calluses, avoidance of exposure of hands and feet to hot water leading to vasodilatation, protection of pressure-sensitive areas of hands and feet, and use of cotton gloves and socks to prevent injury and keep the palms and soles dry.

Early manifestations include tingling, numbness, mild hyperkeratosis, and symmetrical red and swollen areas on the palms and soles. The lateral sides of the fingers or periungual zones may also be affected. Adequate interventions are required to prevent worsening of skin symptoms

such as blisters, desquamations, ulcerations, or necrosis of affected areas. Analgesics may be required for pain control.

Aggressive management of symptoms is recommended, including early dermatology referral. Treatment recommendations in response to PPE are summarized in [Table 6-8](#).

**Table 6-8: Management of Hand-Foot Syndrome (PPE) Associated with Cabozantinib**

CTCAE v5 Grade	Action To Be Taken
Grade 1	Cabozantinib treatment may be continued at the current dose if PPE is clinically insignificant and tolerable. Otherwise, cabozantinib should be reduced to the next lower dose level a . Start urea 20% cream twice daily AND clobetasol 0.05% cream once daily. Reassess at least weekly; if PPE worsens at any time or does not improve after 2 weeks, proceed to the intervention guidelines for Grade 2.
Grade 2	Cabozantinib treatment may be continued if PPE is tolerated. Cabozantinib should be dose reduced or interrupted if PPE is intolerable. Continue urea 20% cream twice daily AND high potency steroid cream (eg, clobetasol 0.05%) once daily and add analgesics (eg, NSAIDs/gamma-aminobutyric acid agonists) for pain control if needed. Reassess at least weekly; if PPE worsens or affects self-care, proceed to the intervention guidelines for Grade 3.
Grade 3	Interrupt cabozantinib treatment until severity decreases to Grade 1 or 0. Continue treatment of skin reaction with high potency steroid cream (eg, clobetasol 0.05%) twice daily AND analgesics. Resume cabozantinib at a reduced dose if PPE recovers to Grade $\leq 1$ . Discontinue subject from study treatment if PPE does not improve within 6 weeks.

CTCAE, Common Terminology Criteria for Adverse Events; NSAID, non-steroidal anti-inflammatory drug; PPE, palmar-plantar erythrodysesthesia.

a Permitted dose levels are defined by individual protocols.

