#### **3.6.1 Treatment Discontinuation**

Subjects will receive study treatment until treatment discontinuation for any of the reasons listed below. Subjects may discontinue study treatment and assessments or withdraw their consent to participate in the study at any time without prejudice. If a subject discontinues all study treatment, the reason will be documented in source documents and all study treatment will be stopped. The investigator may also discontinue a subject from all study treatment if in his or her clinical judgment it is in the best interest of the subject or if the subject cannot comply with the protocol. In addition, the Investigator will also discontinue a subject from study treatment upon the Sponsor's request or if the Sponsor chooses to terminate the study.

The following are possible reasons for discontinuation of all study treatment:

- Subject no longer experiences clinical benefit as determined by the Investigator (eg, disease progression [PD] and/or clinical deterioration attributable to PD where either is unlikely to reverse with continued study treatment and/or supportive care).
- Unacceptable side effects the Investigator feels may be due to study treatment. Continuation of one component of the combination study treatment while discontinuing the other will be allowed. The Investigator is encouraged to discuss such circumstances with the Sponsor.
- The investigator feels it is not in the best interest of the subject to continue on study.

CONFIDENTIAL

Protocol XL184-313 Protocol Amendment 3.0  
Page 53 of 193

- Subject participation in another clinical study using an investigational agent, investigational medical device, or other intervention.
- Necessity for treatment with non-protocol systemic anti-cancer therapy.
- Necessity for interrupting all study treatment for greater than 12 weeks for study-treatment related AEs unless approved by the Sponsor. (Note: temporary interruptions of study treatment for greater than 12 weeks due to the effects of COVID-19 and unrelated to AEs are described in [Appendix K](#).)
- Refusal of sexually active fertile subjects to use highly effective methods of contraception (defined in [Appendix D](#)).
- Female subjects who become pregnant.
- Request by the Sponsor
- Unblinding of study treatment by the Investigator (prior to unblinding of study treatment for all subjects)
- Subject request to discontinue all study treatments (with or without concurrent withdrawal of informed consent).

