**6.1.1 Study Treatment: Cabozantinib in Combination with Nivolumab and Ipilimumab or Nivolumab and Ipilimumab**

**6.1.1.1 Cabozantinib (XL184) Tablets**

The Sponsor will provide adequate supplies of cabozantinib, which will be supplied as 20-mg yellow film-coated round tablets. The components of the tablets are listed in [Table 6-1](#).

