## 6.6.2 Management of AEs Associated with Cabozantinib/Placebo

Throughout the remainder of [Section 6](#) the term “cabozantinib” refers to blinded oral study treatment of cabozantinib or cabozantinib-matched placebo. Considerations for management of AEs associated with oral study medication are presented below.

- The assigned dose for cabozantinib is 40 mg qd.
- Two dose reduction levels of cabozantinib (20 mg qd and 20 mg every other day [qod]) are permitted (see [Table 6-4](#)).

CONFIDENTIAL

Protocol XL184-313 Protocol Amendment 3.0  
Page 88 of 193

- Dose modification criteria for treatment-related AEs of cabozantinib are shown in [Table 6-5](#). Grade 1 and tolerable Grade 2 AEs are managed similarly; Grade 3 and intolerable Grade 2 AEs are managed similarly.
- Dose reinstitution and reescalation after dose interruptions and/or reductions:
  - If the subject recovers from his or her toxicities to CTCAE v5  $\leq$  Grade 1 or to the baseline value (or lower) and the AE was unrelated to oral study medication, then oral study medication may be restarted with no change in dose.
  - If the subject recovers from his or her toxicities to  $\leq$  Grade 1 or to the baseline value (or lower) and the AE was deemed related to oral study medication, then cabozantinib may be reinitiated but this must be at a reduced dose (see [Table 6-4](#)).
  - Subjects receiving a dose of 20 mg every other day (qod) may be restarted at the same dose if deemed safe at the discretion of the Investigator. Subjects unable to tolerate a dose of 20 mg qod must discontinue cabozantinib/placebo upon discussion with the Sponsor.
  - Re-escalation to the previous dose may be allowed at the discretion of the Investigator but no sooner than 10 days beyond improvement of AEs that led to the dose reduction to Grade 1 (or baseline value), as long as AEs are deemed tolerable and easily managed by optimized supportive treatment. Dose reescalation is not allowed following a cabozantinib-related dose reduction for Grade 4 hematologic toxicities or Grade 4 AEs affecting major organs (eg, central nervous system [CNS], cardiac, hepatic, renal, pulmonary GI).

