Subjects with QTc prolongation and symptoms must be monitored closely until the QTc elevation and symptoms have resolved. Cabozantinib treatment may be restarted but only at a reduced dose level if all of the following conditions are met:

CONFIDENTIAL

Protocol XL184-313 Protocol Amendment 3.0  
Page 101 of 193

- Symptoms are determined to be unrelated to the QT interval prolongation
- The QTcF value  $> 500$  ms or increase of  $> 60$  ms above baseline is not confirmed by a **cardiologist consultation**.
- Cabozantinib treatment has been interrupted through a minimum of 1 week following the return of the QTcF to  $\leq 500$  ms and  $\leq 60$  ms above baseline
- Sponsor has reviewed all available information and has agreed to the continuation of study treatment.

Following reinitiation of study treatment, ECGs must be repeated weekly for 2 weeks, then every 2 weeks for 1 month, then according to the protocol-defined time points.

Cabozantinib treatment must be permanently discontinued if either of the following applies:

- Cardiac evaluation confirms that symptoms are the consequence of QT interval prolongation
- Recurrence of QTcF prolongation (confirmed by central ECG lab) after reinitiation of study treatment at a reduced dose

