### 4.1. Definition of Baseline

In general, for efficacy endpoints the last observed measurement prior to randomization will be considered the baseline measurement. An exception to this rule is the efficacy biomarkers such as pharmacogenetics blood samples and plasma biomarker samples. These samples per schedule of assessment are to be collected on Week 1 Day 1 (W1D1) (which could be up to 3 days after randomization) but prior to the administration of the first dose; hence baseline for these measurements will be defined with respect to the first dose date. For subjects who did not take any study treatment, any biomarker sample available prior to randomization will be considered as the baseline observation.

For safety endpoints the last observation on or before first dose of study treatment will be considered the baseline measurement unless otherwise specified and will be established for each period defined in [Section 4.5](#).

For assessments on the day of first dose of study treatment where time is not captured, if such procedures are required by the protocol to be conducted before first dose or a nominal pre-dose indicator is available, this will serve as sufficient evidence that the assessment occurred prior to first dose.

The earliest instance of administration of any agent of study treatment will be considered as the time point of first dose. Similarly, the latest instance of administration of any agent of study treatment will be considered as the time point of last dose of study treatment.

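### The Grade 3 row of Protocol Table 6-8 can be read to stop nivolumab and ipilimumab as well as cabozantinib/placebo for hand-foot syndrome not improved by 6 weeks (minor wording correction)

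*Protocol*

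**What the plan says.** Protocol Table 6-8 sets out the action for each grade of PPE. In the Grade 3 row, the interruption and the reduced-dose resumption both name cabozantinib. The row then ends: "Discontinue subject from study treatment if PPE does not improve within 6 weeks".

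The table belongs to Section 6.6.2, which states its own scope: "Considerations for management of AEs associated with oral study medication are presented below". The same paragraph makes the word *cabozantinib* stand for blinded cabozantinib or placebo through the rest of Section 6. It gives no special meaning to *study treatment*.

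Elsewhere that term covers the regimen. The heading of Protocol Section 6.1.1 reads "Study Treatment: Cabozantinib in Combination with Nivolumab and Ipilimumab or Nivolumab and Ipilimumab". SAP Section 4.1 says: "The earliest instance of administration of any agent of study treatment will be considered as the time point of first dose". On stopping for toxicity, Protocol Section 3.6.1 says: "Continuation of one component of the combination study treatment while discontinuing the other will be allowed".

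**The concern.** The object of the instruction changes within one row, and it changes at the irreversible step. A site that gives *study treatment* its usual meaning would withdraw all remaining drugs from a subject whose Grade 3 PPE has not improved by 6 weeks. Section 6.6 gives hand-foot syndrome as an example of an event caused by cabozantinib.

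Nivolumab and ipilimumab are given in both arms. Ipilimumab ends after four doses, so later in treatment the drug at stake is nivolumab, which the protocol allows for up to 2 years. The possible harm is unnecessary loss of active treatment for an individual subject. It is not a bias in the trial's estimates.

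**Working it through.** No arithmetic applies to the main point. The check compares the sentence with the text that governs it.

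1. **Meaning of the term.** Section 6.1.1, Section 3.6.1 and SAP Section 4.1 all treat *study treatment* as something with several agents or components. Section 6.6.2 narrows *cabozantinib* only. No text narrows *study treatment* to the oral drug within Section 6.6.2.

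2. **Scope of the section.** Section 6.6.2 is limited to events associated with the oral medication. For non-hepatocellular events, Section 6.6 sends cabozantinib/placebo modifications to Section 6.6.2 and nivolumab/ipilimumab modifications to Section 6.6.3. Section 3.6.1 divides the discontinuation criteria in the same way, between Sections 6.6.2 and 6.6.3.2. A rule that ends the antibodies does not belong in Table 6-8.

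3. **Comparison with neighbouring rules.** The other permanent-discontinuation instructions in Section 6.6.2 name cabozantinib or cabozantinib/placebo. They cover intolerance of the minimum dose, Grade 4 events, perforation and fistula, serious hemorrhage, arterial thrombosis, hypertensive emergency, nephrotic syndrome, RPLS and QTc prolongation. Table 6-8 is the exception.

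4. **Other loose uses in Section 6.6.2.** Eight other lines attach a dosing step or condition to *study treatment*: three in Table 6-6, one in 6.6.2.1.4, one in 6.6.2.1.5 and three in 6.6.2.1.15 (3 + 1 + 1 + 3 = 8). Each is resolved by nearby text:
   - *Table 6-6, continue with possible dose reduction, and restart at a reduced dose:* Section 6.6.3 does not allow dose reductions of nivolumab or ipilimumab, so the oral drug is meant.
   - *Table 6-6, interruption:* the diarrhea text in 6.6.2.1.1 that introduces the table names cabozantinib as the drug to interrupt or reduce, and cabozantinib again for retreatment.
   - *6.6.2.1.4, PE/DVT hold:* the next sentence names cabozantinib as the drug that may be resumed.
   - *6.6.2.1.5, blood pressure decisions:* the line speaks of reducing the dose, which only the oral drug permits.
   - *6.6.2.1.15:* "Sponsor has reviewed all available information and has agreed to the continuation of study treatment" is a condition in a list that opens by allowing cabozantinib to restart at a reduced level. "Following reinitiation of study treatment, ECGs must be repeated weekly for 2 weeks" sets the ECG timing after that restart. "Recurrence of QTcF prolongation (confirmed by central ECG lab) after reinitiation of study treatment at a reduced dose" is a trigger in a list that opens by requiring permanent discontinuation of cabozantinib.

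   The Table 6-8 sentence has no such cue of its own. It mentions no dose reduction, and nivolumab and ipilimumab can be discontinued.

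5. **Effect on the analysis.** SAP Table 8 does not list stopping study treatment as an event or a reason for censoring in the primary PFS analysis. Protocol Section 5.7.6.1 continues tumor assessments after treatment stops. The OS analysis is by ITT with a treatment-policy approach. Alpha, power and the event targets (249 PFS events, 433 deaths) do not depend on this sentence.

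**The case against.** The strongest reply is that the intent is clear. The table title, the rest of the row and the stated scope of Section 6.6.2 all point to the oral drug. Where the protocol wants everything stopped, it usually says *all study treatment* or *all study drugs*, as in Sections 3.5.2, 3.6.1, 6.6, 6.6.1 and 6.6.3.2.1 and in Table 6-3. Table 6-8 has no *all*. Section 6.6.2.1.7 introduces the table as treatment recommendations, and Section 6.6.2.1 is headed as management guidelines.

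Most of this stands. It makes the oral-only reading the likely one, and it is why the point is minor. It does not remove the point. The sentence is imperative, under a column headed as action to be taken, and it governs a permanent step. Section 3.6.1 permits a component to continue but does not say that this permission overrides a specific instruction. The reader has to infer the scope, when two words would state it.

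**Conclusion.** The point holds as a minor, optional correction to one sentence. As written, the Grade 3 row of Table 6-8 is ambiguous about whether nivolumab and ipilimumab stop with the oral drug, and the broader reading conflicts with the protocol's own division of rules by drug. The conclusion rests on the term's ordinary use in these documents. It does not assume that any site took the broader reading, and nothing in the documents shows that one did. They give no rate of Grade 3 PPE unimproved at 6 weeks, so the number of subjects affected cannot be estimated.

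A reader might infer more, in two ways that the documents do not support:

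- *That the drugs covered by the Table 6-6 interruption and the PE/DVT hold are unsettled, so that the sponsor must first confirm them.* Sections 6.6.2.1.1 and 6.6.2.1.4 name cabozantinib for the same steps.
- *That Table 6-6 conflicts with Table 6-10, by continuing treatment in tolerable Grade 2 diarrhea when Table 6-10 delays the antibodies for drug-related Grade 2 diarrhea.* Section 6.6 applies Section 6.6.2 to cabozantinib/placebo and Section 6.6.3 to the antibodies, so each table governs its own drugs.

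**What to change.** In the last sentence of the Grade 3 row of Table 6-8, make *cabozantinib/placebo* the object of the discontinuation, in place of the subject's study treatment. Leave the 6-week condition unchanged. The eight lines listed above may be brought into the same terminology in the same amendment. That is for consistency and is not needed to settle their meaning.

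No safeguard is lost. A skin event judged related to nivolumab or ipilimumab remains under Table 6-10.

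The cost is a few words in the next amendment. Section 14 requires IRB/EC submission, with approval before implementation unless a change removes an immediate hazard or is purely logistical or administrative. No change to the SAP is needed.
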